**Describe the following:**

**What type of data and/or events will be reviewed under the monitoring plan, e.g. adverse events, protocol deviations, aggregate data?**

--Primary and secondary outcome measures --Safety/drug use measures --Adverse events (AE), Serious adverse events (SAE), Unanticipated Problem (UP), & Unanticipated Adverse Device Effect (UADE)  
Inclusion/exclusion criteria

**Identify who will be responsible for Data and Safety Monitoring for this study, e.g. Stanford Cancer Institute DSMC, an independent monitoring committee, the sponsor, Stanford investigators independent of the study, the PD, or other person(s).**

The ME is a group of outside and inside experts that includes the PD in the areas clinical trials and biostatistics that reviews the progress of the study and monitors patient enrollment, outcomes, adverse events, and other issues related to patient safety. The ME makes recommendations to the PI as to whether the study should continue or be modified or terminated. The ME can consider patient safety or other circumstances as grounds for early termination, including either compelling internal or external evidence of treatment differences or infeasibility of addressing the study hypotheses (e.g., poor patient intake, poor adherence to the protocol). The ME will meet for every patient to review data reports prepared by our staff. There is continuous communication between the two members of ME and PI and study staff. Any member of the ME can ask for a meeting of the group if he/she feels that it is necessary, based upon the data. The VA SPIRE REHAB committee did not assign an outside DMC for this study as it is a smaller pilot study. The VA SPIRE committee in Rehab is the main regulatory body and monitors it via annual progress reports.

**Title :** Repetitive Transcranial Magnetic Stimulation to Improve Cognitive Function in TBI  
**Approval Period:** 12/11/2018 - 02/13/2019

**Provide the scope and composition of the monitoring board, committee, or safety monitor, e.g., information about each member's relevant experience or area of expertise. If the Monitor is the Stanford Cancer Center DSMC or the PD, enter N/A.**

[name] [name] – Neurologist, expertise in clinical trials and rTMS [name] – Neurologist, expertise in TBI

**Confirm that you will report Serious Adverse Events (SAEs), Suspected Unexpected Serious Adverse Reactions (SUSARs), or Unanticipated Problems (UPs) to the person or committee monitoring the study in accordance with Sponsor requirements and FDA regulations.**

AE - within 48 hours; SAE - within 48 hours; UP - within 5 days

**If applicable, how frequently will the Monitoring Committee meet? Will the Monitoring Committee provide written recommendations about continuing the study to the Sponsor and IRB?**

There is no outside DMC assigned by the VA for this grant. All monitoring is done by PI and ME and the VA Rehab SPIRE progress reports.

**Specify triggers or stopping rules that will dictate when the study will end, or when some action is required. If you specified this in Section 2g [Study Endpoints], earlier in this application enter 'See 2g'.**

We will suspend enrollment if 10 participants experience a seizure (not including syncope) during study participation, and request that the ME evaluate the data, to determine if enrollment of new patients should be resumed without protocol changes, if protocol modifications should be made before resuming enrollment, or if the study should be terminated. We recognize that study termination or modification based on serious adverse events, such as seizures, ultimately rests with the DMC and the study PI and that more stringent stopping points may be initiated during the study. If a patient is determined to be suicidal, either based on the CSSRS, HRSD, clinical evaluation, or by statements made by the patient, a clinical evaluation will be immediately conducted by the Principal Investigator, by the patient's individual mental health provider, or a mental health emergency clinician. The patient will not be left alone until the evaluation has been completed and a decision made about disposition in conjunction with the Chief of Mental Health Outpatient Clinic or the Mental Health Emergency clinician. For alcohol/drug use, stopping criteria for treatment will include: 1. Alcohol use greater than one glass of wine/day or equivalent. Use of alcohol when patient has been warned of serious medication/alcohol interactions, will also fit these criteria. If patients are found to be noncompliant with this, the Principal Investigator will decide whether to administer treatment and evaluate the patient's appropriateness for continued participation. 2. Abuse of illegal drugs. If patients are found to be noncompliant with this, the Principal Investigator will decide whether to administer treatment and evaluate the patient's appropriateness for continued participation. 3. Abuse or misuse of prescribed medications will also result in either withdrawal from the study or inclusion as a noncompliant patient.

**Indicate to whom the data and safety monitoring person, board, or committee will disseminate the outcome of the review(s), e.g., to the IRB, the study sponsor, the investigator, or other officials, as appropriate.**

ME review of all events will be communicated to the IRB when appropriate, via recommended protocol changes or a submitted report through the eProtocol system.

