## 8. Participant Population

- a) **State the following: (i) the number of participants expected to be enrolled at Stanford-affiliated site(s); (ii) the total number of participants expected to enroll at all sites; (iii) the type of participants (i.e. students, patients with certain cancer, patients with certain cardiac condition) and the reasons for using such participants.**

(i) 100 participants are expected to be enrolled  
(ii) 100 participants at VAPAHCS  
(iii) all participants will be Veterans, Military personnel and Civilians.

- b) **State the age range, gender, and ethnic background of the participant population being recruited.**

Age range: 20-65 years  
Note: We may include participants between 65-70 if they contact us and pass the screening (and are not showing cognitive decline related to dementia)  
Gender: Males and Females  
Ethnic Background: Any race or ethnic origin

- c) **State the number and rationale for involvement of potentially vulnerable subjects in the study (including children, pregnant women, economically and educationally disadvantaged, decisionally impaired, homeless people, employees and students). Specify the measures being taken to minimize the risks and the chance of harm to the potentially vulnerable subjects and the additional safeguards that have been included in the protocol to protect their rights and welfare.**

Children, pregnant women, economically and educationally disadvantaged, decisionally impaired, and homeless people will not be recruited for this protocol.

- d) **If women, minorities, or children are not included, a clear compelling rationale must be provided (e.g., disease does not occur in children, drug or device would interfere with normal growth and development, etc.).**

There will be no participation of children in this study.

- e) **State the number, if any, of participants who are laboratory personnel, employees, and/or students. They should render the same written informed consent. If payment is allowed, they should also receive it. Please see Stanford University policy.**

It is unlikely that any laboratory personnel, employees, or students will qualify for participation in this study. If any do qualify and wish to participate, they will be treated the same as any other participant.

**Title :** Repetitive Transcranial Magnetic Stimulation to Improve Cognitive Function in TBI  
**Approval Period:** 12/11/2018 - 02/13/2019

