**The risks of the Investigational drugs. Information about risks can often be found in the Investigator's brochure.**

n/a

**The risks of the Commercially available drugs, reagents or chemicals. Information about risks can often be found in the package insert.**

n/a

**The risks of the Procedures to be performed. Include all investigational, non-investigational and non-invasive procedures (e.g., surgery, blood draws, treadmill tests).**

rTMS - rTMS Safety especially for Mild and Moderate TBI Veterans

After a decade of research, rTMS is generally regarded as safe and without lasting side effects if established guidelines are followed (Janicak et al., 2008; Machii et al., 2006). There have been no significant cognitive (Triggs et al., 1999; Little et al., 2000), neurological (Nahas et al., 2000) or cardiovascular sequelae reported as a result of rTMS.

The primary safety concern with rTMS, in any population, has been the risk of seizure induction. Eight seizures have been reported secondary to rTMS (Wassermann, 1998). These have occurred in a sample size estimated to be over several thousand rTMS treatment sessions. The rTMS community has adopted and widely used the guidelines prescribing a safe interval between pulse trains (Gerloff et al., 1997) and the safety guidelines from a National Institute of Neurological Disorders and Stroke (NINDS) workshop on rTMS. To our knowledge there have been two publications since 1997 describing events during rTMS that might be considered seizures. Conca and colleagues reported a patient who experienced a 'pseudoabsence seizure'. It is unclear if this was a true seizure (Conca et al., 2000). Bernabeu and colleagues reported on a patient who had a seizure during rTMS. In this case, there was a brief interstimulus interval (Bernabeu et al., 2004). The risk of seizures for rTMS treatment is less than 1%.

How does this impact our study: The current safety guidelines have not been tested for mild and moderate TBI population which is precisely the purpose of this pilot grant. In TBI population, posttraumatic epilepsy

**Title :** Repetitive Transcranial Magnetic Stimulation to Improve Cognitive Function in TBI  
**Approval Period:** 12/11/2018 - 02/13/2019

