is the most common delayed sequelae of TBI. But this incidence is very low (about 5%) in TBI patients with closed head injury (Ropper et al., 2005) who are most likely our mild and moderate TBI patients. In a clinical setting, for example in Polytrauma Transitional Rehabilitation Program (PTRP – VAPA) the expected recovery trajectory for persons with mTBI is full cognitive recovery in 3-6 months following injury. Persisting or worsening cognitive status is often related to other co-morbid psychiatric issues, such as depression and PTSD, chronic pain, sleep apnea (all will be) used as covariates in our analysis). Including persons with moderate TBI in our study would likely allow for examination of rehabilitation treatment effects on cognitive functioning for those who tend to have persisting cognitive difficulties following injury. On PTRP, patients are often admitted from the acute inpatient rehab unit on anticonvulsant medications if they had a seizure 1 day or more following the injury. Typically, if the patient experienced a seizure immediately at the scene of the incident, they are not considered at a greater risk for subsequent seizures. For those who do not have a history of seizures following injury, they are not considered at a greater risk of subsequent seizures and are not placed on anticonvulsant medications. Importantly, the interval between the head injury and the first seizure varies greatly (Demirtas-Tatlidede et al., 2012) and must be considered as a variable for recruitment in this study. Currently PTRP houses patients 2 months to 2 years post TBI. Note, that there is only one case study which performed detailed safety assessments and reported a lack of adverse events in a patient with severe TBI following application of a specific rTMS protocol over 5 consecutive days through 6 weeks (Pape et al., 2009). Our protocol will be highly stringent and will exclude any severe TBI patients (including those with any fractures, metal plates or open head injuries), acute patients or those who have had a concussion within the last 2 months, and those who have a history of seizures of any type.

Neuropsychology testing - The risks posed by neuropsychological testing are mild frustration and mild fatigue that will not persist.

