**rTMS**

In the unlikely event that a seizure does occur, the participant will be closely monitored and treated for any medical or psychological consequences. Lab tests will be drawn and the participant will be seen by a neurologist as soon as possible. The facility where the rTMS studies are performed is fully equipped to safely handle a seizure. The participant will be given a letter regarding the seizure to share with his or her primary health care provider. The letter will indicate that the seizure during rTMS does not increase risk for future seizures.

rTMS treatment can result in mild to moderate headaches in as many as 30 out of 100 of patients. Some people also report discomfort at the site of rTMS stimulation. This occurs in around 15 out of 100 of patients. Headaches and site discomfort usually readily respond to acetaminophen or ibuprofen. Painfulness improves over time or goes away. Often patients fall asleep in the second week while receiving the same treatment that on the first day was reported as very painful.

There is a small risk of dental pain with rTMS, during or immediately after the treatment. If this occurs, study staff may be able to move the rTMS coil position or provide a bite block to reduce this pain or make it not happen.

rTMS treatment may produce movement or tingling of the arm, leg, face or scalp. Participants may also experience a temporary feeling of numbness in the face.

**Title :** Repetitive Transcranial Magnetic Stimulation to Improve Cognitive Function in TBI  
**Approval Period:** 12/11/2018 - 02/13/2019

There is a possible risk of hearing loss due to the light clicking sounds made by the device. Participants will wear earphones during rTMS sessions. This should greatly reduce the possibility of hearing loss. Hearing will be tested at baseline, after the intervention phase, and after follow-up to see if any hearing loss has occurred.

The rTMS operator will monitor all participants for ear protection, coil placement, and seizure activity during all sessions.

- d) Explain the point at which the experiment will terminate. If appropriate, include the standards for the termination of the participation of the individual participant Also discuss plans for ensuring necessary medical or professional intervention in the event of adverse effects to the participants.**

The clinical trial will terminate after 2 years or when 40 participants have been through the protocol.

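### The only mandatory seizure pause is set at 10 participants, 10 to 25 times the count expected at the protocol's own 1% ceiling, and some safety decisions are assigned to a DMC that the monitoring plan does not contain

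*Protocol*

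**What the plan says.** **The trigger.** Section 9(e) of the Protocol, in answer to the question on triggers or stopping rules, states: "We will suspend enrollment if 10 participants experience a seizure (not including syncope) during study participation". The ME then reviews the data and advises whether to resume, modify or terminate. The text allows stricter stopping points to be introduced during the study but fixes none.

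**The risk.** Section 9(a), under rTMS, calls seizure induction the primary safety concern and says "The risk of seizures for rTMS treatment is less than 1"%. Of the population under study it says "The current safety guidelines have not been tested for mild and moderate TBI population". On post-traumatic epilepsy it adds: "But this incidence is very low (about 5%) in TBI patients with closed head injury".

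**The sample size.** Section 8(a) says "100 participants are expected to be enrolled". Section 9(d) says "The clinical trial will terminate after 2 years or when 40 participants have been through the protocol", and section 8(g) and the Resources item on sufficient time also work with 40. Both sizes are carried below.

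**The monitors.** Section 9(e) says "The ME is a group of outside and inside experts that includes the PD" and "The ME will meet for every patient to review data reports prepared by our staff". It states that the VA assigned no outside DMC and that monitoring is done by the PI, the ME and VA progress reports. Yet section 2(g) has a DMC set the reporting schedule, decide when it is unblinded for adverse event review, and advise the PI on stopping. The stopping-rule text in 9(e) leaves final authority over termination or modification with the DMC and the PI.

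**The concern.** A fixed count in a stopping rule exists so that a pause does not depend on anyone's judgement once the evidence is strong. It therefore has to lie where the evidence first departs clearly from the assumed risk. Ten participants is far beyond that point: the rule would stay silent at seizure rates several times the stated ceiling, in a population for which the protocol itself says the safety guidelines are untested.

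The second problem is who decides. If a seizure raises the question of unblinding, section 2(g) sends it to a body that section 9(e) does not include among the monitors. The same body shares the last word on stopping.

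**Working it through.** The protocol gives no derivation for 10, so there is no stated calculation to reproduce. The check compares the trigger with the protocol's own risk figures.

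**Inputs**
- Trigger: 10 participants with a seizure (section 9(e)).
- Risk ceiling: 1% (section 9(a)), read as per participant.
- n = 100 (section 8(a)) or n = 40 (sections 8(g) and 9(d)).
- Background: about 5% post-traumatic epilepsy (section 9(a)). The period is not stated, and section 8(h) excludes a seizure history. It is relevant because the rule counts any seizure during participation.

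**Step 1. Expected counts, n × p**
- At 1%: 100 × 0.01 = 1.0 and 40 × 0.01 = 0.4. The trigger is 10/1.0 = 10 times and 10/0.4 = 25 times the expected count.
- At 5%: 5 and 2. The trigger is still 2 and 5 times the expected count.

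**Step 2. Probability that the pause is ever reached**

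With X ~ Binomial(n, p), the quantity is P(X ≥ 10):

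| True risk | n = 40 | n = 100 |
|---|---|---|
| 1% | 6.4 × 10⁻¹² | 7.6 × 10⁻⁸ |
| 5% | 0.002% | 2.8% |
| 10% | 0.5% | 55% |
| 20% | 27% | 99.8% |

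Solving P(X ≥ 10) = 0.5 gives p = 24.0% (n = 40) and 9.6% (n = 100). Solving for 0.8 gives 29.9% and 12.3%.

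**Step 3. What nine seizures would mean**

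Nine participants mandate no pause.
- 9/40 = 22.5%, exact (Clopper-Pearson) 95% interval 10.8% to 38.5%.
- 9/100 = 9.0%, interval 4.2% to 16.4%.

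The lower limits are about 11 and 4 times the 1% ceiling. At a true 5% risk, the chance of ending with 2 to 9 seizures and no mandated pause is 60% (n = 40) or 93% (n = 100).

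**Step 4. Sensitivity to who is exposed**

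The trial has a sham arm, and the allocation ratio is not stated. Assuming 1:1 and counting only active participants, the exposed number is 20 or 50. An even chance of reaching 10 then needs a true risk of 47.5% or 19.2%. Counting everyone as exposed, as in steps 1 to 3, is therefore generous to the rule.

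**Step 5. Sensitivity to the unit of the 1%**
- If 1% were per session over the 20 sessions in section 2(a), the per-participant risk would be 1 − 0.99²⁰ = 18.2%. With 1:1 allocation that gives 50 × 0.182 = 9.1 or 20 × 0.182 = 3.6 affected active participants, and P(X ≥ 10) = 43% or 0.1%.
- Section 9(a) also cites eight seizures in several thousand sessions. Taking 2,000 to 5,000 sessions as an assumed range, the per-session risk is 0.4% to 0.16%, and over 20 sessions 1 − (1 − 8/2000)²⁰ = 7.7% to 1 − (1 − 8/5000)²⁰ = 3.2% per participant. That gives 3.9 to 1.6 of 50 active participants, or 1.5 to 0.6 of 20, still well short of 10.

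**Step 6. The monitoring texts side by side**

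| Decision | Assigned to | Where |
|---|---|---|
| Reporting schedule, unblinding for adverse events, advice on stopping | DMC | 2(g) |
| Evaluation after the seizure trigger | ME | 9(e), stopping rules |
| Final authority on termination or modification | DMC and PI | 9(e), next sentence |
| All monitoring | PI, ME, VA progress reports | 9(e), monitoring plan |

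The document never says that the ME is the DMC, and the stopping-rule text names both in adjacent sentences.

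**The case against.** The strongest reply is that 10 is only a backstop. The ME meets for every patient, any member can call a meeting, it may recommend stopping on safety grounds, and serious adverse events are reported within 48 hours. Section 9(c) requires prompt neurological review after a seizure. Nine seizures would not pile up unseen. This stands as a description of review, and it makes an unexamined run of seizures unlikely. It does not supply a threshold: none of these steps requires enrolment to pause, and the ME includes the PD, so the discretion is not fully independent.

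The unit of the 1% is also a fair point. The multiples of 10 and 25 depend on the per-participant reading, and at 1% per session the ratios fall to about 1.1 (50 active) and 2.7 (20 active). That extreme fits poorly with the protocol's own count of eight seizures in several thousand sessions.

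The figures for n = 40 may reflect text not updated to the current target of 100. That is possible, but section 9(d) still stands, and the rule is also badly placed at n = 100.

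Two attachments listed in section 16, a seizure protocol and a safety protocol, are not available and may contain further criteria. The point is therefore limited to the number in section 9(e).

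On the DMC, the text denies only an outside committee, and the monitoring plan does identify the ME. The gap is thus narrow, but it covers unblinding and shared final authority, which should not be left to inference.

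**Conclusion.** The concern holds and should be fixed. As written, the sole mandatory seizure pause would almost never operate at five times the stated ceiling (2.8% chance at n = 100, 0.002% at n = 40), and needs a true risk of about 10% to 24% for an even chance of operating. This rests on reading the 1% as per participant, on independent participants with a common risk, and on counting all enrolled as exposed; the last of these favours the rule. Only the extreme reading of 1% per session with 50 active participants brings the expected count near 10. Whether 10 is a typing error cannot be told from the document. The conflict between the DMC and ME wording is textual and needs no assumption.

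**What to change.** In section 9(e), replace 10 with a low count derived from the stated risk and the number exposed. State the unit of the 1%, say whether sham participants count, and print the operating characteristics beside the rule. For illustration, the probability of a pause with all enrolled counted:

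| Pause at | n | 1% | 5% | 10% |
|---|---|---|---|---|
| 2 participants | 40 | 6.1% | 60% | 92% |
| 2 participants | 100 | 26% | 96% | >99.9% |
| 3 participants | 40 | 0.7% | 32% | 78% |
| 3 participants | 100 | 7.9% | 88% | 99.8% |

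This points to 2 if the trial stops at 40 and 3 if it enrols 100. Holding the chance of a pause at a true 1% risk to at most 5% gives 3 (0.7%) and 4 (1.8%) instead. The choice within 2 to 4 belongs to the monitors.

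In sections 2(g) and 9(e), replace the DMC by the ME, including for the decision to unblind adverse event data. Because the ME includes the PD, state which of its members may see unblinded data.

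**Cost.** Protocol wording and a short table. There may be an unnecessary pause: 6.1% to 26% with a count of 2 and 0.7% to 7.9% with a count of 3 at a true 1% risk. If background seizures approached 5%, the 5% column would apply and a pause would be likely in most cases. It is a pause for review, not a termination.

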**Secondary Hypotheses:**

1. Sustained Improvement. At the end of the 6-month post treatment follow-up, TBI patients who received rTMS would be more likely to continue to have reduced symptoms, i.e. greater "executive function improvement" than patients who received sham rTMS.
2. Secondary consequences of TBI will improve with rTMS treatment, i.e. scores on Quality of Life (QOL) scale will show significantly greater improvement in patients with mild to moderate TBI who received rTMS treatment.
3. Moderators of Response. Age, severity of symptoms at baseline, type of comorbidity (PTSD, time since injury, sleep, depression substance abuse, medication use, cognitive exercises, fatigue or any combinations of these), TBI type, duration of

**Title :** Repetitive Transcranial Magnetic Stimulation to Improve Cognitive Function in TBI  
**Approval Period:** 12/11/2018 - 02/13/2019

illness and prior treatment resistance (rTMS/ECT): may affect or "moderate" treatment response.

4. Greater functional connectivity will be observed in hub centers of the Default Mode Network (DMN), particularly the precuneus/posterior cingulate area as measured by resting state fMRI at follow-up compared to baseline in those TBI patients treated with rTMS compared to those treated with sham.

5. Mediators of Response to Treatment: to establish a preliminary understanding of the underlying mechanisms related to rTMS modulation of synaptic repair in TBI we will also look at Brain Derived Neurotrophic Factor (BDNF) plasma samples in our population.

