**2. Study Procedures**

- a) **Please SUMMARIZE the research procedures, screening through closeout, which the human subject will undergo. Refer to sections in the protocol attached in section 16, BUT do not copy the clinical protocol. Be clear on what is to be done for research and what is part of standard of care.**

List of Procedures for the rTMS protocol:

Screening Measures:

- Telephone screening call: 1 hr
- Consenting and on-site screening: approx. 6 hrs
- Physical exam, medical history
- Medication review
- Interviews, self-report questionnaires  
Clinical TBI Evaluation
- Blood (60 cc), urine, and breath tests
- Determination of TMS motor threshold (markings on the cap will be marked with "MT" for motor threshold and "Tx" for treatment site.
- Eligibility determination
- Randomization to active or sham treatment

Baseline measures: approx. 8 hrs

- Interviews, self-report questionnaires, tasks (pain, fatigue, sleep, malingering, depression, PTSD, TBI, suicide, cognition);
- Cognitive testing (including main outcome measure for executive function) and webneuro computerized testing
- Neuroimaging: Diffusion Tensor Imaging (DTI), functional MRI (fMRI); structural MRI
- If indicated, and prior to MRI scan, an MRI X-ray screen will be performed if there is suspicion that participant may have metal in their body
- Pure Tone Audiometry

Intervention Measures:

- rTMS or sham treatment: up to 3 treatments a day for up to 5 days/week, 2-6 weeks = 20 sessions. Each session lasting 30-60 minutes in length. Depending on schedule, and at the physician's discretion, up to three rTMS sessions can be scheduled per day with a one hour interval between sessions, shortening treatment duration to 1.5 weeks.
- TMS motor threshold determination prior to the first treatment and every 5th day of treatment thereafter (at least weekly).
- Random breathalyzer and urine tests will be administered during the intervention phase to screen for drug and alcohol use; depending on results, participant may not be allowed to receive

**Title :** Repetitive Transcranial Magnetic Stimulation to Improve Cognitive Function in TBI  
**Approval Period:** 12/11/2018 - 02/13/2019

additional rTMS treatment for safety reasons

- Blood samples (60 cc) will be taken every 10 rTMS

treatment

for processing of BDNF from blood plasma.

- Headache and Pain self report will be recorded before and after every treatment session.

Follow-up (post treatment and 6 months): approx. 8.5 hrs

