- Interviews, Self-Report Questionnaires (same as above);
- Pure Tone Audiometry;
- Cognitive testing including executive function main

outcome measure and webneuro computerized testing

• Neuroimaging: Diffusion Tensor Imaging (DTI), Functional MRI (fMRI), structural MRI

• Blood samples (60 cc) will be taken for processing of BDNF from blood plasma.

- b) Explain how the above research procedures are the least risky that can be performed consistent with sound research design.**

The study design involves minimal risk to participants. This research project is a placebo control study design.

- c) State if deception will be used. If so, provide the rationale and describe debriefing procedures. Since you will not be fully informing the participant in your consent process and form, complete an alteration of consent (in section 13). Submit a debriefing script (in section 16).**

Deception will not be used.

- d) State if audio or video recording will occur. Describe what will become of the recording after use, e.g., shown at scientific meetings, erased. Describe the final disposition of the recordings.**

None will occur.

- e) Describe alternative procedures or courses of treatment, if any, that might be advantageous to the participant. Describe potential risks and benefits associated with these. Any standard treatment that is being withheld must be disclosed in the consent process and form. (i.e. standard-of-care drug, different interventional procedure, no procedure or treatment, palliative care, other research studies).**

There are many alternative procedures/courses of improving executive function including cognitive training, weight loss, exercise, etc although their clinical feasibility can be questioned. No standard treatments for improving executive function are being withheld from potential participants in this study.

- f) Will it be possible to continue the more (most) appropriate therapy for the participant(s) after the conclusion of the study?**

If rTMS is found to be effective for improving cognitive function, it may be possible to have patients return for booster sessions.

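### A treatment-stopping rule allows randomised participants to be withdrawn from the study, with no criterion, so their outcome scores may never be collected

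*Protocol*

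**What the plan says.** The rule is in the Data Safety and Monitoring Plan (protocol section 9e), in the answer on triggers and stopping rules. The list opens with "For alcohol/drug use, stopping criteria for treatment will include" and has three items.

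- **Items 1 and 2 (alcohol; illegal drugs).** For a noncompliant participant, "the Principal Investigator will decide whether to administer treatment and evaluate the patient's appropriateness for continued participation".
- **Item 3 (prescribed medication).** "Abuse or misuse of prescribed medications will also result in either withdrawal from the study or inclusion as a noncompliant patient". Misuse is not defined, no decision-maker is named, and no criterion separates the two outcomes.

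Section 2a (Study Procedures) also deals with substance use during treatment: "Random breathalyzer and urine tests will be administered during the intervention phase to screen for drug and alcohol use". The stated consequence there concerns stimulation alone: "depending on results, participant may not be allowed to receive" additional rTMS. Leaving the study is not mentioned.

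Section 2a places randomisation at the end of screening, before the intervention phase. After baseline, the remaining assessments are listed under "Follow-up (post treatment and 6 months): approx. 8.5 hrs", and they include "Cognitive testing including executive function main" outcome measure.

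**The concern.** Stopping an intervention and stopping follow-up are separate decisions. Section 9e announces the first and then, in item 3, permits the second. Items 1 and 2 join the two in a single judgement by the Principal Investigator.

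A participant taken off stimulation can still attend the post-treatment and 6-month visits. A participant withdrawn from the study would, as the rule is worded, have no post-treatment score for the primary hypothesis and no 6-month score for the durability hypothesis. A statistical analysis plan can define analysis sets and missing-data methods, but it cannot supply scores that were never collected. The matter therefore belongs to the protocol.

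The loss may be informative. The moderator hypothesis in section 1b names, among the factors that may affect response, "sleep, depression substance abuse, medication use, cognitive exercises, fatigue or any combinations of these". The rule could therefore remove people on characteristics that the trial itself suspects are related to outcome.

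**Working it through.** The protocol gives no expected number of such withdrawals, no dropout rate and no power calculation, so there is no figure to reproduce. The check compares the text and then gives a labelled illustration of size.

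**Text**

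1. *Type of rule.* Section 9e introduces criteria for stopping treatment, but item 3's stated outcomes are leaving the study or staying in it as noncompliant. For data collection these are opposites.
2. *Consistency.* For a positive drug or alcohol test, section 2a provides only for withholding further rTMS. Staff following 2a would stop stimulation and keep assessing. Staff following 9e could remove the person altogether.
3. *Timing.* Randomisation comes before the intervention phase in which the random tests are done, so the rule can act on randomised participants. Those on a stable psychotropic regimen are eligible (section 8h), so item 3 can apply to people in the trial.
4. *Safeguard.* Nothing in the document provides for assessing participants who have been withdrawn from the study.

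**Illustration of size**

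Inputs from the protocol:
- total 40 (section 9d) or total 100 (section 8a).

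Assumptions, with no source in the protocol:
- 1:1 allocation, giving 20 or 50 per arm
- 1 to 3 participants lost per arm
- 30% responders
- a 20-point lower response rate among those lost, where loss is informative.

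*Share of an arm unobserved per lost participant:* 1/20 = 5%; 1/50 = 2%. For three lost, 15% or 6%.

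*Loss unrelated to outcome.* There is no bias, only less precision. The standard error of the difference in responder proportions is √(2 × 0.3 × 0.7 / n) = √(0.42 / n):

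| Planned per arm | SE, none lost | SE, 3 lost per arm |
|---|---|---|
| 20 | √(0.42/20) = 14.5 points | √(0.42/17) = 15.7 points |
| 50 | √(0.42/50) = 9.2 points | √(0.42/47) = 9.5 points |

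*Loss related to outcome, one arm only.* If m of n are lost and would respond g points less often than the rest, the observed rate in that arm is too high by (m/n) × g:
- 20 per arm: (3/20) × 20 = 3.0 points
- 50 per arm: (3/50) × 20 = 1.2 points
- with g = 0, the bias is 0.

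*Loss related to outcome, equal in both arms with the same gap.* Under no treatment effect the two shifts cancel and the bias in the difference is zero.

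**The case against.** The strongest reply is that the rule already contains its remedy. One of item 3's outcomes keeps the participant in the trial as noncompliant, items 1 and 2 do not order withdrawal, and nothing requires outcomes to go uncollected. Read with the list's introduction and with section 2a, withdrawal from the study may be loose wording for withdrawal from treatment. That reading is possible, but the literal words authorise the other one, and staff have no instruction on which to follow.

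Second, few participants should trigger the rule. Section 8h excludes current substance abuse within 3 months before screening and asks for a psychotropic regimen stable for at least 4 weeks. Treatment lasts about 1.5 to 6 weeks (section 2a). The breathalyzer and urine tests are described as screening for drug and alcohol use, not specifically for misuse of prescriptions, so the evidence on when item 3 would be triggered is indirect. All of this stands, and it limits the size of the problem.

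Third, the document is an application form with attachments that are not shown, including a safety protocol and the grant. One of them might provide for follow-up after withdrawal. That is possible, but it would not remove the ambiguity in section 9e.

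Fourth, the illustrative figures rest on assumed inputs, and the 3.0-point case needs all the losses to fall in one arm. Nothing in the protocol shows that the choice would depend on arm or on outcome scores. This is correct, and no such claim is made.

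Finally, an investigator needs discretion over safety. The proposed wording leaves the discretion to withhold treatment intact.

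**Conclusion.** The point holds as a minor defect that is worth correcting. Section 9e allows a randomised participant to be removed from the study under a rule introduced as a treatment-stopping rule, gives no criterion for doing so, and sits poorly with section 2a, which provides only for withholding stimulation. The consequence is a possibility, since the alternative branch retains the participant.

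The size is likely to be small, and its direction is unknown. On the stated assumptions it ranges from no bias with a slightly larger standard error (14.5 to 15.7 points at 20 per arm; 9.2 to 9.5 at 50) to a bias of 3.0 or 1.2 points if three informative losses fall in one arm. The conclusion rests on the literal reading of withdrawal from the study and on no unseen attachment providing follow-up after withdrawal.

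**What to change.** In section 9e, limit all three criteria (alcohol, illegal drugs, prescribed medication) to stopping or withholding rTMS, at the Principal Investigator's discretion. Replace the references to withdrawal from the study and to continued participation with wording such as: *Treatment may be stopped or withheld. The participant remains in the post-treatment and 6-month assessments unless consent is withdrawn, is recorded as noncompliant, and is analysed in the arm to which he or she was randomised.*

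This brings section 9e into line with section 2a. The cost is a change of protocol wording and the effort of following a few noncompliant participants at visits that are already scheduled.
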